- Mini-open carpal tunnel release through a 2–3 cm incision in a minor procedure room, under full aseptic technique; hemostasis via epinephrine-induced vasoconstriction and meticulous technique.

Arm B – Local Anesthesia With Tourniquet (LA-T)

- 20 mL of 1% lidocaine (200 mg) buffered identically but without epinephrine.
- Infiltrated approximately 5 minutes before incision in the operating room.
- A blood-pressure cuff tourniquet placed above the elbow (no exsanguination), inflated to 100 mmHg above systolic pressure after arm elevation and draping, released after skin closure.
- Mini-open carpal tunnel release through a 2–3 cm incision under standard aseptic conditions.

Two experienced surgeons (orthopedic hand consultant and neurosurgery peripheral nerve specialist) performed all procedures; each performed approximately 50 cases.

8. Outcomes

Primary Outcome

- Overall intraoperative pain (VAS 0–10): patient's rating of pain during the entire surgery, assessed immediately after surgery by a blinded assessor.

Secondary Outcomes

- Infiltration pain (VAS 0–10): pain during local anesthetic injection.
- Tourniquet pain (VAS 0–10): tourniquet-specific pain in LA-T group.
- Operative time (minutes): from skin incision to completion of skin closure.
- Patient satisfaction (0–10 scale): global satisfaction with the operating-room experience.
- Intraoperative complications: bleeding requiring intervention, nerve injury, or other deviations from normal course.

Demographics: age, sex, BMI, ASA class, CTS-6 severity score.

9. Sample size

A target sample of 100 patients (50 per arm) was chosen based on feasibility at the two centers and expected medium effect size in intraoperative pain VAS. Post-hoc analysis showed that with 50 participants per group and the observed

effect size (Cohen's $d \approx 0.75$), power was approximately 94% (two-sided $\alpha = 0.05$) to detect the group difference in intraoperative pain.

10. Randomization and allocation concealment

- Simple computerized randomization with 1:1 allocation to WALANT or LA-T.
- Randomization list held by an investigator ([name]) not involved in surgery or postoperative assessment.
- On the day of surgery, the investigator informed the operating surgeon of the assigned technique after consent, maintaining concealment before enrollment.

11. Blinding

- Patients were not explicitly told which anesthetic technique they received.

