Subset excluding major deviations (e.g., cross-over of anesthetic technique, incomplete surgery) if any occurred. Primary inferences will be based on ITT; PP will be supportive.

3. General statistical principles

- Two-sided tests with significance level $\alpha = 0.05$.
- Continuous variables: reported as mean \pm SD if approximately normal, or median (IQR) if skewed.
- Categorical variables: counts and percentages with 95% confidence intervals.
- Normality checked with Shapiro–Wilk test and inspection of histograms.
- Main analyses non-parametric where distribution assumptions are not met; parametric tests may be reported as sensitivity analyses.
- Statistical software: SPSS version 29.

4. Baseline characteristics

Baseline demographics and clinical characteristics (age, sex, BMI, ASA class, CTS-6 score) will be summarized by group using descriptive statistics.

- Continuous variables: compared using independent-samples t-test or Mann–Whitney U test as appropriate.
- Categorical variables: compared using chi-square or Fisher’s exact test as appropriate.
These comparisons are descriptive; no p-value adjustment is planned as they are not hypothesis-driven.

5. Primary outcome analysis

Outcome: Overall intraoperative pain VAS (0–10).

- **Primary analysis method:**
Mann–Whitney U test comparing VAS scores between WALANT and LA-T.
- Effect size:
 - Median difference with 95% CI.
 - Non-parametric effect size measure (e.g., rank-biserial correlation) as reported; you previously used effect size ≈ 0.63 with 95% CI.

- **Sensitivity analysis:**
Independent-samples t-test (parametric), assuming approximate normality, to corroborate non-parametric findings.

No adjustment for multiple testing is applied to the primary endpoint.

6. Secondary outcomes analysis

1. Infiltration pain VAS (0–10)

- Analysis: Mann–Whitney U test comparing WALANT vs LA-T.
- Report: medians (IQR), means (SD), p-value, and effect size.

2. Tourniquet pain VAS (LA-T only)

- Descriptive analysis within LA-T arm: median (IQR), distribution plots.
- No between-group statistical test (not defined in WALANT arm).

3. Operative time (minutes)

- Analysis: Mann–Whitney U test for group comparison.
- Report: median (IQR) per group, p-value, effect size.

4. Patient satisfaction (0–10)

- Analysis: Mann–Whitney U test to compare satisfaction scores between groups.
- Report: median (IQR), p-value, and effect size.

5. Intraoperative complications

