- Analysis: counts and proportions in each group; Fisher’s exact or chi-square test if sufficient events.
- Given low expected event counts, analysis is primarily descriptive.

Multiplicity:

Secondary outcomes are interpreted cautiously; no formal adjustment for multiple comparisons. Emphasis remains on the primary outcome.

7. Subgroup analyses

Pre-specified subgroups:

- Age group: <65 vs ≥65 years.
- Sex: male vs female.
- Surgeon: Orthopedic (Surgeon A) vs Neurosurgery (Surgeon B).

For each subgroup:

- Compare intraoperative VAS between WALANT and LA-T using Mann–Whitney U test within strata.
- Test for interaction (e.g., using non-parametric interaction tests or rank-based methods) to assess whether the treatment effect differs by age, sex, or surgeon; manuscript reported non-significant interactions (age p=0.45, sex p=0.82, specialty p=0.76).

Subgroup findings are exploratory and hypothesis-generating.

8. Handling of missing data

- Missing primary outcome data are expected to be rare because VAS is collected immediately postoperatively.
- If isolated missing VAS values occur, primary analysis will be complete-case (excluding those without any intraoperative VAS value). Given small numbers, imputation is unlikely to materially change results.
- If >5% of participants lack primary outcome data, a sensitivity analysis using simple imputation (e.g., median of group) may be explored, but the main report will transparently present complete-case results.

9. Sensitivity and additional analyses

- **Timing of anesthetic administration:**
Exploratory analyses to assess whether variation in injection-to-incision time confounds results; previous sensitivity analysis showed no meaningful pattern.
- **Post-hoc power:**
Based on observed effect (mean 0.80 vs 2.08, pooled SD 1.52), Cohen's $d \approx 0.75$, and $n=50$ per group, post-hoc power $\approx 94\%$ ($\alpha=0.05$).
- **Graphical displays:**
Box plots and distribution plots for VAS scores, operative time, and tourniquet pain; subgroup plots by age, sex, and surgeon.

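### SAP 9 states d ≈ 0.75, but its own means and SD give 0.84; the 94% power built on that d is post hoc and cannot support the sample size

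*Combined protocol and SAP*

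**What the plan says.** Protocol section 9 (Sample size) says that 100 patients, 50 per arm, was "chosen based on feasibility at the two centers and expected medium effect size in intraoperative pain VAS". It gives no number for that effect, no SD and no target power. It then reports, as a post-hoc result at an observed d of about 0.75, that "power was approximately 94" per cent.

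SAP 9 repeats the 94% and adds the inputs: "Based on observed effect (mean 0.80 vs 2.08, pooled SD 1.52", with d again about 0.75 and 50 per group.

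SAP 5 makes the Mann–Whitney U test the primary analysis, with a t-test as sensitivity analysis. Under effect size, beside the example of a rank-biserial correlation, it carries the remark "you previously used effect size ≈ 0.63 with 95% CI" and does not say which statistic the 0.63 is.

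**The concern.** The means, the SD and d stand together in SAP 9, and d is just the mean difference divided by the SD. The printed values do not satisfy that relation. All of them describe the primary endpoint, so the error touches the main effect estimate that readers will take from the trial.

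The second problem is how the 94% is used. It is the only power figure in either document, and it stands in the sample size section of a protocol dated before enrolment opened. Power evaluated at the observed effect is a restatement of the test result: a clearly significant result always yields high observed power. It carries no information about whether 50 per arm was an adequate choice beforehand. Without it, the sample size section contains only feasibility and the word medium.

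**Working it through.** **Inputs.** Means 0.80 and 2.08, pooled SD 1.52, d ≈ 0.75, n = 50 per group (SAP 9). Two-sided α = 0.05 (SAP 3). Allocation 1:1 (protocol section 10). Primary test Mann–Whitney, t-test as sensitivity (SAP 5).

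**Step 1: the plan's own figure, from its stated d.** The noncentrality is d × √(n/2) = 0.75 × 5 = 3.75.
- Normal approximation: Φ(3.75 − 1.96) = Φ(1.79) = 96.3%.
- t-test (noncentral t, 98 df): 96.0%.
- Mann–Whitney, with n multiplied by the relative efficiency 3/π: 95.2%. A 20,000-run simulation under a normal shift gave 95.0%.
- Mann–Whitney at the lower bound of the relative efficiency (0.864): 93.1%.

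So 94% is about 1 to 2 points from what d = 0.75 gives, and lies inside the Mann–Whitney range of 93.1% to 95.2%.

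**Step 2: d from the quoted means and SD.** d = (2.08 − 0.80)/1.52 = 1.28/1.52 = 0.842. Rounding does not explain the gap: the smallest value is 1.27/1.525 = 0.83 and the largest 1.29/1.515 = 0.85. To reach 0.75, the SD would have to be 1.28/0.75 = 1.71, or the difference 0.75 × 1.52 = 1.14.

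**Step 3: power from the quoted means and SD.** The noncentrality is 0.842 × 5 = 4.21.
- Normal approximation: Φ(4.21 − 1.96) = Φ(2.25) = 98.8%.
- t-test: 98.6%.
- Mann–Whitney: 98.3% (simulation 98.2%; 97.2% at the efficiency lower bound).

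None of these is 94%, and all are above it.

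**Step 4: precision from the quoted figures.** SE = 1.52 × √(2/50) = 0.304. The 95% CI is 1.28 ± 1.984 × 0.304 = 1.28 ± 0.60, or 0.68 to 1.88. If the SD were 1.71, the SE would be 0.342 and the interval 0.60 to 1.96. If the difference were 1.14, it would be 0.54 to 1.74.

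**Step 5: illustration under an assumed planning effect.** The documents attach no number to medium. If it meant the conventional d = 0.5 (an assumption), power with 50 per arm is as follows.

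| Assumed d | Mann–Whitney | t-test |
|---|---|---|
| 0.4 | 49% | 51% |
| 0.5 | 68% | 70% |
| 0.6 | 83% | 84% |

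The effect detectable with 80% power by Mann–Whitney is d ≈ 0.58, or 0.58 × 1.52 = 0.88 VAS points.

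These are normal-shift calculations. A mean of 0.80 with a pooled SD of 1.52 on a 0–10 scale implies skewed data, so the power figures are approximate. Step 2 needs no distributional assumption.

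**The case against.** The best defence is that the damage is small. The 94% agrees acceptably with the d printed beside it under the planned test, the documents call it post hoc in both places, and the only broken step is from the means and SD to d. The test, α, the number of patients and the primary analysis are untouched, SAP 5 already asks for an effect estimate with a 95% CI, and every interval in step 4 excludes zero. All of that stands. It limits the point to a correction of reporting and justification; it does not remove the contradiction or supply a prospective basis for the size.

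Three stronger readings are tempting, and the documents do not support them.

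- *The error inflates the power.* It does not. Against the quoted means and SD, 94% is too low, and correcting d to 0.84 would raise the figure.
- *The trial was designed with only 68–70% power.* That treats d = 0.5 as the planning effect. The documents say only "expected medium effect size in intraoperative pain VAS", with feasibility as the other basis, and the plausible range around that convention is wide (49–84%). Equally, 50 per arm does have power of about 93–96% if the true d is 0.75.
- *The 0.63 is a third effect size that conflicts with the others.* Under normality, a d of 0.75 to 0.84 corresponds to a rank-biserial of 2Φ(d/√2) − 1 = 0.40 to 0.45, but the data cannot be close to normal. One integer data set shows that 0.63 is possible. Take WALANT counts at scores 0–6 of 40, 0, 2, 1, 3, 3, 1 (sum of scores 40, mean 40/50 = 0.80) and LA-T counts at 0–4 of 2, 22, 7, 8, 11 (sum 104, mean 104/50 = 2.08). The pooled SD is 1.52 and the rank-biserial 0.629. So 0.63 is unlabelled, but not shown to be wrong.

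**Conclusion.** The point holds in two parts. First, SAP 9 is wrong as written: its means and SD give d = 0.84 (0.83 to 0.85 allowing for rounding), not 0.75, and power of about 98–99%, not 94%. The documents alone cannot show whether a mean, the SD or d is the faulty entry. Second, the 94% in protocol section 9 is an observed-effect calculation and gives the sample size no support, and nothing else there is numerical.

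The first part is plain arithmetic. The power figures rest on normal-shift approximations. The 68–70% rests in addition on reading medium as d = 0.5, and should not be quoted as the trial's planned power. Nothing here suggests that the direction or significance of the primary comparison would change.

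**What to change.** 1. Check both means and the pooled SD against the data. Correct d, or correct the faulty input, in SAP 9 and protocol section 9 so that they agree. If d used a denominator other than the quoted pooled SD, say which.
2. Delete the post-hoc power statement as support for the sample size in both places. State that 100 patients was a feasibility-based number and that no numerical planning effect was recorded.
3. If power is shown at all, present it as a retrospective illustration with the assumption labelled. For example: if medium is taken as d = 0.5, about 68% by Mann–Whitney or 70% by t-test, with about 49–84% over d = 0.4 to 0.6; d of about 0.58 is detectable with 80% power. It should not be written as though it had been a design assumption.
4. Express precision by the confidence interval of the treatment difference (1.28, 95% CI 0.68 to 1.88, subject to item 1), alongside the median difference and interval that SAP 5 already requires.
5. In SAP 5, name the statistic that 0.63 refers to, check it against the data, and give its interval.

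The cost is a short recalculation and a few changed sentences, with no new patients. The downside is that the sample size section loses its favourable 94%.
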